6.3.2 Blinding

Blinding Method

Randomization codes will be kept strictly confidential, accessible only to authorized staff (i.e. randomization statistician, unblinded reconstitution team, bioanalytical laboratories responsible for analyses of the PK samples and unblinded monitor), until the time of unblinding. All other study-related individuals, ancillary site staff, clinical research associates/monitors, the Investigator, Sponsor, ECG core lab, and clinical research organization staff will remain blinded to study intervention.

Since moxifloxacin will be administered open-label, and evobrutinib and placebo administered double-blinded, the treatment sequences will not be displayed in this protocol. Placeholders ('Treatment A', 'Treatment B', 'Treatment C', and 'Treatment D') will be used to refer to the study interventions. Only authorized staff mentioned above will be aware of the sequences actually used.

The procedures of database lock and unblinding statistical analyses will be documented in the Data Management Plan and Unblinding Plan.

Confirmation of the Indistinguishability of the Study Interventions: evobrutinib and placebo solutions will be identical in volume and appearance.

The analytical laboratories responsible for analysis of the PK samples will be unblinded to study treatment codes to enable sample testing of evobrutinib and moxifloxacin prior to database lock. Masked participant identifiers will be used to support association of PK data with treatment codes while preventing association of treatment codes with any other clinical data, such as safety and clinical response data.

Evobrutinib and moxifloxacin information that would unblind the study participants will not be reported with participant identifiers to investigative sites or blinded personnel until the study has been unblinded.

Assignment Method Retention

Unblinding may be done in the event of an emergency necessary for participant safety or the reporting of SUSARs using code break envelopes provided to the site by the CTS department.

6.3.3 Emergency Unblinding

In an emergency, the Investigator is solely responsible for determining if unblinding of a participant's study intervention assignment is warranted. Participant safety is always the first consideration in this decision. If the Investigator decides that unblinding is warranted, the Investigator makes every effort to contact the Sponsor prior to the unblinding, unless this could delay emergency treatment. The Sponsor will be notified within 24 hours after unblinding. The Investigator will provide the Sponsor the reason for unblinding without revealing the study intervention, except to the designated global patient safety representative via the Emergency

Unblinding Notification Form. The date of and reason for unblinding will be recorded in the source documents and CRF. Contact information for unblinding in an emergency is given on the participant emergency card provided to each participant, as noted in [Appendix 2](#).

6.4 Study Intervention Compliance

When participants are dosed at the site, they will receive study intervention directly from the Investigator or designee, under medical supervision. The date and time of each dose administered in the clinic will be recorded in the source documents and recorded in the CRF. A member of the study site staff other than the person administering the study intervention will confirm the study intervention dose and study participant identification at the time of dosing. Study site personnel will examine each participant's mouth to ensure that the study intervention was ingested.

6.5 Dose Modification

Doses will not be modified.

6.6 Continued Access to Study Intervention After the End of the Study

The Sponsor will not provide any additional care to participants after they leave the study because such care would not differ from what is normally expected for healthy participants.

6.7 Treatment of Overdose

For this study, any dose of study intervention greater than maximum dose that is considered safe and well-tolerated within a 24 hour time period will be considered an overdose.

The Sponsor has no specific recommendation for treating an overdose of evobrutinib or moxifloxacin. The Investigator will use his/her clinical judgment to manage any overdose, considering the symptoms and any site procedures or standards.

Even if not associated with an AE or SAE, any overdose is recorded in the CRF and reported to global patient safety in an expedited manner. Overdoses are reported on an SAE and Overdose Report Form, following the procedure in [Appendix 4](#).

6.8 Concomitant Therapy

Record in the CRF all concomitant therapies (e.g. medicines or nondrug interventions) used from the signing of the ICF until the end of treatment assessment at the timepoints specified in the SoA, including any changes. For prescription and over-the-counter medicines, vaccines, vitamins, and herbal supplements, record the name, reason for use, dates administered, and dosing information. For nondrug interventions, record the name, the indication, and dates administered.

Contact the Medical Monitor for any questions on concomitant or prior therapy.

Paracetamol/Acetaminophen, at doses of ≤ 2 g/24 hours, is permitted for use any time during the study, at the discretion of the Investigator. Other concomitant medication may be considered on a case-by-case basis by the Investigator in consultation with the Medical Monitor if required.

6.8.1 Rescue Medicine

No specific antidote is available for evobrutinib. Symptomatic treatment will be provided in case of a medical emergency. Any kind of toxicity occurring during the study will be treated symptomatically.

In case of toxicity during moxifloxacin, refer to the approved product information.

6.8.2 Permitted Medicines

The only permitted medicines are the following:

Acetaminophen (paracetamol) up to 2 g per day, at the discretion of the Investigator.

Any medicines that are considered necessary to protect the participant's welfare in emergencies may be given at the Investigator's discretion, regardless if it results in a protocol deviation.

6.8.3 Prohibited Medicines

Prohibited medicines at study entry are indicated in the exclusion criteria (Section 5.2).

The participants are prohibited from using prescription or over-the-counter medications (apart from those described above) within 2 weeks or 5 terminal half-lives, whichever is longer, prior to the first administration of study intervention, during the study, and until the Safety Follow-Up assessment (this includes herbal remedies, vitamins, minerals, antacids, and dietary supplements such as fish oils).

Inhibitors or inducers of CYP3A4/5 or P-gp within 4 weeks prior to the first administration of study intervention, and until after the Safety Follow-Up assessment, are prohibited. Also, drugs mainly metabolized by CYP3A4/5 and that have a narrow therapeutic index should be avoided.

6.8.4 Other Interventions

Additional restrictions that study participants should adhere to from Day -1 until the Final assessment are detailed in Section 5.2.

7 Discontinuation of Study Intervention and Participant Discontinuation/Withdrawal

Discontinuation of specific sites or of the entire study is specified in Appendix 2.

7.1

Discontinuation of Study Intervention

A participant must be withdrawn from administration of study intervention if any of the following occur:

- Participant withdraws consent.
- A participant is enrolled but is subsequently discovered not to have met inclusion/exclusion criteria at Screening.
- AEs, if discontinuation of study intervention is considered necessary by the Investigator and/or desired by the participant. This includes in particular AEs of severe intensity and SAEs regardless of the relationship to study intervention.
- Pregnancy (see Section 8.3.4).
- Protocol noncompliance judged as significant by the Investigator (after discussion with the Sponsor).
- Use of a nonpermitted concomitant drug if clinically relevant as agreed by Sponsor and Investigator, as defined in Section 5.2, where the predefined consequence is withdrawal from study intervention.
- Any events that unacceptably endanger the safety of the participant.

If study intervention is permanently discontinued, the participant will remain in the study to be evaluated for safety assessments: The SoA indicates data to be collected at the time of discontinuation of study intervention and follow-up and for any further evaluations that need to be completed.

The SoA specifies the data to collect at study intervention discontinuation and follow-up, and any additional evaluations that need to be completed.

7.1.1

Liver Clinical Safety Laboratory Tests Stopping Criteria

The Investigator will consider discontinuation of study intervention for abnormal liver function when a participant meets one of the conditions outlined in the algorithm or if the Investigator believes that it is in best interest of the participant.

All confirmed events of ALT or AST $\geq 5 \times$ ULN triggers stopping criteria.

All confirmed events of ALT or AST $\geq 3 \times$ ULN and total bilirubin $\geq 2 \times$ ULN triggers stopping criteria.

All liver related events will be reported as AESI according to the risk profile of evobrutinib.

7.1.2

Cardiac Safety Stopping Criteria

If a clinically significant finding is identified (including changes from baseline in QT interval corrected using Fridericia's formula [QTcF > 60 ms and QT/QTcF > 500 ms]) after start of study intervention, the Investigator or qualified designee will determine if the participant can continue

in the study and if any change in participant management is needed. This review of the ECG at the time of collection will be documented. Any new clinically relevant finding is reported as an AE.

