	
18. Clinically relevant findings (excluding minor, not clinically relevant excursions from normal ranges, as judged by the Investigator) at Screening in biochemistry, hematology, coagulation, and urinalysis examinations for the age of the participant, as judged by the Investigator:
 
• Alanine aminotransferase, aspartate aminotransferase: above ULN• Creatinine: above normal limits• Absolute lymphocyte count, absolute neutrophil count: below limit of reference range.• Amylase and lipase above normal ranges, minor deviations are allowed, if not clinically relevant.• Abnormal, low levels of potassium levels
	
19. Estimated glomerular filtration rate according to the Chronic Kidney Disease Epidemiology Collaboration Creatinine Equation (2009) < 90 mL/min at Screening. In case of a borderline result between ≥ 80 and < 90 mL/min, Cystatin C will be determined in addition, and the participant will only be included if the Cystatin C value is below the upper limit of normal.

	
20. Semi-supine systolic blood pressure > 140 mmHg or < 90 mmHg, diastolic blood pressure > 90 mmHg or < 50 mmHg, and pulse rate > 90 or < 50 bpm at Screening. Any abnormal blood pressure results may be repeated once and if the repeat result is within the normal range, it is not considered to have met the exclusion criterion.

	
21. 12-Lead ECG showing a QT interval corrected for heart rate according to Fridericia's formula (QTcF) > 450 ms, PR > 215 ms, or QRS > 110 ms at Screening.

	
22. Any other abnormal laboratory results that the Investigator believes should preclude the participant's participation in the study.

Other Exclusions	
23. Consumption of an average weekly alcohol intake of > 14 units/week for men or > 7 units/week for women. 1 unit (12 g) of alcohol equals $\frac{1}{2}$ pint (285 mL) of beer or lager, 1 glass (125 mL) of wine, or $1/6$ gill (25 mL) of spirits.

Category	Criterion
	24. Contraindication to moxifloxacin (refer to approved product information moxifloxacin).
	25. Excessive consumption of xanthine-containing food or beverages (> 5 cups of coffee a day or equivalent) or inability to stop consuming caffeine, from 48 hours prior to study intervention administration until after collection of the final PK sample in each period.
	26. Consumption of alcohol from 48 hours prior to first administration of study intervention.

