16.3.4.3 By Timepoint and Categorical Analysis

The Safety analysis set will be used for the analysis.

Triplet 10 s ECGs from continuous Holter recordings for central evaluation will also be extracted and evaluated statistically similar to standard safety ECG described in section 15.5.1. For the evaluation of continuous variables, the mean of each assessment at each time point with triplicates will be used in summary tables and for the evaluation of qualitative variables, the worst assessment will be used in summary tables, if not stated otherwise. Change from baseline will also be calculated and summarized.

This Holter ECG assessment include the parameters QT, QTcB, PR, QRS, RR, HR, and cardiologist assessment including T-wave morphology, and U-wave.

QTcI will be derived by log-linear regression. Individual correction factors (m_i) for log-transformed QT vs. log-transformed RR data for each subject at predose (-1 h, -30 min, -10 min) and from the placebo period will be fitted. QTcI will then be calculated as shown in [Equation 2](#)

$\Delta\Delta QTcF$, $\Delta\Delta QTcI$, $\Delta\Delta HR$, $\Delta\Delta PR$, $\Delta\Delta RR$, $\Delta\Delta QRS$, will be calculated as the difference between the change from baseline of active treatment (evobrutinib or moxifloxacin) and the time-matched change from baseline of placebo.

For $\Delta\Delta QTcF$, the postdose timepoint with the maximum mean for each active study intervention will be selected and tabulated together with the mean value and its 2-sided 90% confidence intervals (CI).

QT values will be categorized for each time point using the following groups

- ≤ 500 ms
- > 500 ms

Observed QTcF values will be categorized according to their absolute values into the categories

- ≤ 450 ms
- > 450 and ≤ 480 ms,
- > 480 and ≤ 500 ms, and
- > 500 ms,

and categorized according to their absolute change from baseline into the categories

- ≤ 30 ms,
- > 30 and ≤ 60 ms, and
- > 60 ms.

The number and percentage of subjects by these categories at each postdose assessment will be tabulated by study intervention.

A categorical analysis for outliers will be performed in order to identify the frequency of postdose categorical outliers for ECG parameters by study intervention:

The categorical outliers for HR parameters will be categorized as:

- HR changes reflecting at least a 25% decrease from baseline to a $HR < 50$ beats per minute (bpm) (Bradycardic event)

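### The only numeric cardiac prompt in Protocol 7.1.2 treats 500 ms as a change from baseline and joins it to the 60 ms limit with *and*

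*Protocol*

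**What the plan says.** Protocol 7.1.2 opens with a general trigger, "If a clinically significant finding is identified", and then gives examples, "including changes from baseline in QT interval corrected using Fridericia's formula", followed by the bracketed limits "QTcF > 60 ms and QT/QTcF > 500 ms". When the trigger is met, "the Investigator or qualified designee will determine if the participant can continue" in the study, and the ECG review is documented.

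Three other places bear on the reading:

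- **Protocol 7.1.1**, the liver rule immediately above, uses *and* for a true joint condition, pairing ALT or AST with bilirubin: "ULN and total bilirubin $\geq 2 \times$ ULN triggers stopping criteria". Its alternative trigger stands in a separate sentence.
- **Protocol 5.2**, exclusion criterion 21, sets an entry ceiling: "QTcF) > 450 ms, PR > 215 ms, or QRS > 110 ms at Screening". It applies at Screening only.
- **SAP 16.3.4.3** tabulates absolute QT and absolute QTcF with a top category above 500 ms. Separately, QTcF values are "categorized according to their absolute change from baseline into the categories", the highest of which is above 60 ms.

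**The concern.** Both limits fall under the phrase about change from baseline. Nothing marks the 500 ms limit as absolute, and the phrase names only corrected QT although the bracket also includes uncorrected QT. Read literally, the second limit can never be reached. A site must therefore decide what was meant, and two repairs are open to it: two separate limits, or two limits that must both be met. They give different answers for the same ECG.

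This matters because 7.1.2 governs the documented decision on whether a healthy participant continues after a marked QT change. The study deliberately gives a QT-prolonging control, has no data and safety monitoring committee (Protocol 4.1), and is a four-period crossover, so a participant with a finding in the first period may face three more doses. I found no other on-treatment numeric QT limit that prompts action: criterion 21 applies at Screening, and the SAP categories are for tabulation.

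**Working it through.** The plan gives no figure to reproduce. The check compares the possible readings of 7.1.2.

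**Inputs**

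- Limits of 60 ms and 500 ms: Protocol 7.1.2.
- Fridericia correction, QTcF = QT / RR^(1/3) with RR = 60/HR: SAP 16.3.3. Rearranged, QT = QTcF × (60/HR)^(1/3).
- Screening QTcF ceiling of 450 ms and screening pulse range of 50 to 90 bpm: Protocol 5.2, criteria 21 and 20.
- Baseline QTcF of 380, 400, 420 and 440 ms, and post-dose heart rates of 50, 55 and 60 bpm or faster: illustrative assumptions. The documents give no baseline QTcF distribution.

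**Reading 1, literal (500 ms as a change).** From 400 ms, QTcF would have to exceed 400 + 500 = 900 ms; from 450 ms, 450 + 500 = 950 ms. This limit cannot function.

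**Reading 2, joint (500 ms absolute, *and* as a conjunction).** Let either QT or QTcF satisfy the 500 ms limit. The QTcF at which uncorrected QT equals 500 ms is 500 / (60/HR)^(1/3):

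| Heart rate | (60/HR)^(1/3) | QTcF when QT = 500 ms |
|---|---|---|
| 50 bpm | 1.0627 | 470.5 ms |
| 55 bpm | 1.0294 | 485.7 ms |
| 60 bpm | 1.0000 | 500.0 ms |
| 90 bpm | 0.8736 | 572.4 ms |

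At 60 bpm or faster QTcF reaches 500 ms no later than QT does, so QTcF governs. Below 60 bpm QT gets there first. The QTcF rise that must be exceeded before both limits are met is

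rise = max(60, min(500, 500 / (60/HR)^(1/3)) − baseline).

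| Baseline QTcF | 60 bpm or faster | 55 bpm | 50 bpm |
|---|---|---|---|
| 380 ms | 120 ms | 105.7 ms | 90.5 ms |
| 400 ms | 100 ms | 85.7 ms | 70.5 ms |
| 420 ms | 80 ms | 65.7 ms | 60 ms |
| 440 ms | 60 ms | 60 ms | 60 ms |

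The lowest baseline from which a rise of just over 60 ms is enough is 500 − 60 = 440 ms at 60 bpm or faster, 485.7 − 60 = 425.7 ms at 55 bpm, and 470.5 − 60 = 410.5 ms at 50 bpm.

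**Reading 3, separate limits (as in SAP 16.3.4.3).** A rise above 60 ms is enough at every baseline and heart rate, and so is any absolute QT or QTcF above 500 ms.

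**Two cases under readings 2 and 3**

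- QTcF from 400 to 470 ms, a rise of 70 ms, at 60 bpm: met under separate limits (70 > 60). Not met under joint limits, because QT and QTcF are both 470 ms.
- QTcF from 450 to 505 ms, a rise of 55 ms: met under separate limits (505 > 500). Not met under joint limits (55 < 60).

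**The case against.** The strongest reply is that this is loose drafting with no practical effect.

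- After *including*, the word *and* ordinarily joins items in a list. The liver rule is a direct statement of a criterion, so its use of *and* does not settle the meaning inside an illustrative parenthesis.
- A medically qualified reader would never adopt a 500 ms change, and the mention of uncorrected QT hints at an absolute limit. The SAP confirms that intent.
- The trigger is any clinically significant finding, so a 70 ms rise that stays below 500 ms remains open to review on every reading. The adverse event rules and the withdrawal criteria in 7.1 still apply.
- Meeting the limits forces no stop, because the investigator decides.
- The rises in the table measure only the joint reading, at assumed baselines.

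Most of this stands. It shows that oversight is not missing, and it limits the weight of the point. It does not make the sentence usable. Where the decision rests on judgement, the numeric limits are the one anchor that does not. Here they are impossible if read literally and ambiguous once repaired. The SAP shows what was probably meant, but the site works from the protocol.

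**Conclusion.** The point holds: the bracket in 7.1.2 is wrong as written and should be corrected. On the joint reading, at 60 bpm or faster, the numeric prompt is delayed from a rise above 60 ms to one above 80 to 120 ms for baselines of 420 down to 380 ms. There is no delay from 440 ms upwards. At 55 bpm the corresponding range is about 66 to 106 ms, and at 50 bpm about 60 to 91 ms.

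These sizes assume that 500 ms is absolute, that both limits must be met, that either QT or QTcF may meet the second, and that the illustrative baselines and heart rates apply. They say how far the two repairs differ, not how many participants would be affected; the documents support no such share. The fault is a misworded safety prompt. Investigator oversight remains in place, and neither the SAP categories nor the primary concentration-QTc analysis is at fault.

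**What to change.** Reword the bracket in Protocol 7.1.2 to: *including an increase from baseline in QTcF > 60 ms, or an absolute QT or QTcF > 500 ms*. The rest of the paragraph can stay, including the general trigger and the investigator's decision. The cost is one line in a protocol amendment, with no new assessment and no change to the SAP.

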7.1.3 Hypersensitivity/Allergic Reactions Stopping Criteria

Hypersensitivity, allergic reactions and Severe Cutaneous Adverse Reactions have been reported for fluoroquinolones, including moxifloxacin, after first administration. In cases of clinical manifestations of severe hypersensitivity reactions or signs and symptoms of severe skin reactions Participant should be discontinued from the study.

7.2 Participant Discontinuation/Withdrawal from the Study

- A participant may discontinue from the study at any time, at his/her own request or at the discretion of the Investigator for safety, behavioral, compliance, or administrative reasons (e.g. disruption of operations due to natural disasters, interruption of lab or facility accreditation, participant moving to another country, resignation of key staff").
- At the time of study discontinuation, if possible, a discontinuation visit will be conducted, as listed in the SoA. The SoA specifies the data to collect at study discontinuation and follow-up, and any additional evaluations that need to be completed.
- If the participant revokes consent for the study, any data collected up to that point may still be used, but no future data can be generated, and any biological samples collected will be destroyed.
- If a participant requests the destruction of any biological samples still remaining, the Investigator will document this in the site study records and inform the Sponsor. The samples will be destroyed.

7.3 Lost to Follow-Up

A participant will be considered lost to follow-up if he or she repeatedly fails to return for scheduled visits and is unable to be contacted by the study site.

The following actions will be taken if a participant fails to return to the clinic for a required study visit:

- The site will attempt to contact the participant and reschedule the missed visit as soon as possible, counsel the participant on the importance of maintaining the assigned visit schedule and ascertain if the participant wants to or will continue in the study.
- Before a participant is deemed "lost to follow-up", the Investigator or designee will make every effort to regain contact with the participant: 1) where possible, make 3 telephone calls; 2) if necessary, send a certified letter (or an equivalent local method) to the participant's last known mailing address, and 3) if a participant has given the appropriate consent, contact the participant's general practitioner or caretaker (where allowed by local regulations) for information. These contact attempts will be documented in the participant's medical record.
- If the participant continues to be unreachable, he/she will be deemed as "lost to follow-up".

8

Study Assessments and Procedures

- Study assessments and procedures and their timing are summarized in the SoA.
- **No** protocol waivers or exemptions are allowed.
- Immediate safety concerns are discussed with the Sponsor immediately upon occurrence or awareness to determine if the participant will continue or discontinue study intervention.
- Adherence to the study design requirements, including those specified in the SoA, is essential and required for study conduct.
- All screening evaluations will be completed and reviewed to confirm that potential participants meet all eligibility criteria. The Investigator will maintain a screening log to record details of all participants screened, to confirm eligibility, and if applicable, record reasons for screening failure.
- Prior to performing any study assessments that are not part of the participant's routine medical care, the Investigator will obtain written informed consent as specified in [Appendix 2](#).
- Procedures conducted as part of the participant's routine medical care (e.g. blood count) and obtained before signing of the ICF may be used for screening or baseline purposes provided the procedures met the protocol-specified criteria, were performed within the time frame defined in the SoA, and if reviewed and approved by the Sponsor.
- Any data (including Safety, PK and ECG data) that could unblind the study will not be reported to investigative sites or other blinded personnel until the study has been unblinded.
- About 450 ml of blood total will be taken throughout the study. Up to 100 ml of blood may be drawn at certain visits. These blood samples will be used for the following purposes: clinical laboratory tests and PK analyses.

Where allowed by local law/regulations, samples collected during this clinical study may be transferred to a biobank and used for future research outside the clinical protocol when additional consent for this purpose is given. Transfer to the biobank will be documented and any testing of coded biobank samples will **not** be reported in the CSR.

8.1

Efficacy Assessments and Procedures

Not applicable

8.2

Safety Assessments and Procedures

The safety profile of the study intervention will be assessed through the recording, reporting and analysis of baseline medical conditions, AEs, physical examination findings, vital signs, electrocardiograms, and laboratory tests.

Comprehensive assessment of any potential toxicity experienced by each participant will be conducted starting when the participants give informed consent and throughout the study. The Investigator will report any AEs, whether observed by the Investigator or reported by the participant; the reporting period is specified in Section [8.3](#).

